6.4.1 Criteria for Permanent Withholding of AMG 427 due to Potential Hepatotoxicity

Investigational product should be discontinued permanently and the subject should be followed according to the recommendations in [Appendix A](#) (Additional Safety Assessment Information) for possible drug-induced liver injury (DILI), if ALL of the criteria below are met:

- Increased AST or ALT from the relevant baseline value as specified below:

Baseline AST or ALT value	AST or ALT elevation
< ULN	> 3x ULN

AND

- TBIL > 2x upper limit of normal (ULN) or INR > 1.5

AND

- No significant elevation of ALP ($\leq 2x$ ULN)

- No other cause for the combination of the above laboratory abnormalities is immediately apparent including pre-existing or acute liver disease. Important alternative causes for elevated AST/ALT and/or elevated TBIL values include, but are not limited to:
 - hepatobiliary tract disease
 - viral hepatitis (eg, hepatitis A/B/C/D/E, Epstein-Barr Virus, cytomegalovirus, herpes simplex virus, varicella, toxoplasmosis, and parvovirus)
 - right sided heart failure, hypotension or any cause of hypoxia to the liver causing ischemia
 - exposure to hepatotoxic agents/drugs including herbal and dietary supplements, plants, and mushrooms
 - heritable disorders causing impaired glucuronidation (eg, Gilbert's syndrome, Crigler-Najjar syndrome) and drugs that inhibit bilirubin glucuronidation (eg, indinavir, atazanavir)
 - alpha-1 antitrypsin deficiency
 - alcoholic hepatitis
 - autoimmune hepatitis
 - Wilson's disease and hemochromatosis
 - nonalcoholic fatty liver disease including steatohepatitis (NASH)
 - non-hepatic causes (eg, rhabdomyolysis, hemolysis)

6.4.2 Criteria for Conditional Withholding of AMG 427 due to Potential Hepatotoxicity

For subjects who do not meet the criteria for permanent discontinuation of AMG 427 outlined above and have no underlying liver disease and eligibility criteria requiring normal transaminases and TBIL at baseline or subjects with underlying liver disease and baseline abnormal transaminases, the following rules are recommended for withholding of Amgen investigational product and other protocol-required therapies:

- Elevation of either AST or ALT according to the following schedule:
 - Any AST or ALT elevation: $> 8 \times \text{ULN}$ at any time
 - Any AST or ALT elevation: $> 5 \times \text{ULN}$ but $< 8 \times \text{ULN}$ for ≥ 2 weeks
 - Any AST or ALT elevation: $> 5 \times \text{ULN}$ but $< 8 \times \text{ULN}$ and unable to adhere to enhanced monitoring schedule
 - Any AST or ALT elevation: $> 3 \times \text{ULN}$ with clinical signs or symptoms which are consistent with hepatitis (such as right upper quadrant pain/tenderness, fever, nausea, vomiting, or jaundice).
- OR: TBIL $> 3 \times \text{ULN}$ at any time
- OR: ALP $> 8 \times \text{ULN}$ at any time

AMG 427 should be withheld pending investigation into alternative causes of the laboratory elevations. If the investigational product is withheld, the subject is to be followed according to recommendations in [Appendix A](#) for possible DILI. Rechallenge may be considered if an alternative cause for impaired liver tests (ALT, AST, ALP) and/or elevated TBIL level is discovered and the laboratory abnormalities resolve to normal or baseline (Section [6.4.3](#)).

Discontinuation of the product should be considered and the decision to re-challenge should be discussed with the Amgen medical monitor before re-initiating treatment with investigational product.

6.4.3 Criteria for Rechallenge of AMG 427 After Potential Hepatotoxicity

If signs or symptoms recur with rechallenge, then the investigational product should be permanently discontinued. Subjects who clearly meet the criteria for permanent discontinuation (as described in Section [6.4.1](#)) should not be rechallenged.

6.5 Concomitant Therapy

Throughout the study, Investigators may prescribe any concomitant medications or treatments deemed necessary to provide adequate supportive care except for those listed in Section [6.9](#). COVID-19 vaccine administration (if applicable) should be captured in the concomitant medications.

Concomitant therapies are to be collected from informed consent, through the SFU or LTFU, as applicable. For all concomitant therapies **including vaccines**, collect therapy name, indication, dose, unit, frequency, route, start date, and stop date.

6.5.1 Vaccines

Every effort should be made to fully vaccinate subjects prior to 14 days from first dose of AMG 427. The use of vaccines except live vaccines will be allowed during therapy per regional and institutional standard of care. However, SARS-CoV-2 vaccinations should be avoided during screening (within a minimum of 14 days from first dose of AMG 427) and should be also avoided in the first treatment cycle for better assessment of safety parameters. Throughout the trial, SARS-CoV-2 vaccination should be avoided within 3 days after the administration of AMG 427. In the event where a subject requires steroids for treatment of adverse events, vaccination should be avoided while on steroids.

Table 5. Management of COVID-19

Grade	Interruption/Delay	Specific Management	Re-start guidance	Permanent Discontinuation
SARS-CoV-2 infection and COVID-19 disease				
Asymptomatic	Interruption required until at least 10 days since positive SARS-CoV-2 test UNLESS patient previously fully vaccinated against SARS-CoV-2. If patient previously vaccinated and tests positive, then discuss with Medical Monitor.	Follow local guidelines and standard of care for COVID-19 treatment and isolation Contact Amgen Medical Monitor within 1 business day to ensure appropriate documentation & management of study activities	
 • Re-start possible upon agreement between Investigator and Amgen Medical Monitor provided: 
 ○ There are no new findings on physical exam related to SARS-CoV-2, AND ○ Subject tests negative for SARS-CoV-2 by RT-PCR, OR 
 ○ If subject continues to test positive for SARS-CoV-2 more than 10 days after initial positive test, or If subject initially tests positive in the setting of prior COVID vaccination, resume investigational product only after discussion with patient and reassessment of individual risk/benefit • Consider chest imaging, EKG, ECHO, and cardiology assessment • Consider hospitalization for re-start of investigational product based on length of treatment interruption, risk of CRS at restart, and amount of time since patient was last treated • Dose modification: resume at the same dose or reduce to next lower dose if clinically indicated • Premedication and assessments: follow guidance in schedule of assessment tables 	Immediately stop the infusion (if applicable) and permanently discontinue investigational product therapy IF: Subject required treatment interruption greater than 28 days and upon discussion with Amgen Medical Monitor the decision is made to permanently discontinue treatment OR Initial benefit/risk assessment for individual patient is not maintained any longer

Footnotes defined on next page of the table

Table 5. Management of COVID-19

Grade	Interruption/Delay	Specific Management	Re-start guidance	Permanent Discontinuation
SARS-CoV-2 infection and COVID-19 disease				
Symptomatic	Interruption required until at least 10 days since complete resolution of acute symptoms	Interruption required until at least 10 days since complete resolution of acute symptoms	
 • Re-start possible upon agreement between Investigator and Amgen Medical Monitor provided: 
 ○ There are no new findings on physical exam and chest imaging, related to SARS-CoV-2, ○ Subject tests negative for SARS-CoV-2 by RT-PCR, OR 
 ○ If subject continues to test positive for SARS-CoV-2 more than 10 days after initial positive test, resume investigational product only after discussion with patient and reassessment of individual risk/benefit • Consider chest imaging, EKG, ECHO, and cardiology assessment • Consider hospitalization for re-start of investigational product based on length of treatment interruption, risk of CRS at restart, and amount of time since patient was last treated • Dose modification: resume at the same dose or reduce to next lower dose if clinically indicated • Premedication and assessments: follow guidance in schedule of assessment tables 	Immediately stop the infusion (if applicable) and permanently discontinue investigational product therapy IF Subject required treatment interruption greater than 28 days due to severe or life-threatening COVID-19 OR Initial benefit/risk assessment for individual patient is not maintained any longer

COVID-19 = coronavirus-19; CRS = cytokine release syndrome; ECHO = echocardiography; EKG = electrocardiogram; RT-PCR = reverse transcriptase-polymerase chain reaction; SARS-CoV-2 = severe acute respiratory syndrome coronavirus 2

6.6 Specific Recommendations for Cytokine Release Syndrome, Immune-effector Cell-associated Neurotoxicity Syndrome, Tumor Lysis Syndrome and Infection Prophylaxis

Cytokine Release Syndrome

Cytokine release syndrome is clinically defined and may have various manifestations. There are no established diagnostic criteria. Signs and symptoms of CRS may include:

- Constitutional – fever, rigors, fatigue, malaise
- Neurologic – headache, mental status changes, dysphasia, tremors, dysmetria, gait abnormalities, seizure
- Respiratory – dyspnea, tachypnea, hypoxemia
- Cardiovascular – tachycardia, hypotension
- Gastrointestinal – nausea, vomiting, transaminitis, hyperbilirubinemia
- Hematology – bleeding, hypofibrinogenemia, elevated D-dimer
- Skin – rash

Cytokine release is an anticipated consequence of T cell engagement induced by AMG 427. Cytokine release syndrome, including serious events **and a fatal event**, has been reported **in subjects** receiving AMG 427 in the clinical trial. Subjects may be at an increased risk for CRS during the first few days following the initial dose of AMG 427 and after a dose step. **More severe cases of CRS and/or ICANS have also been associated with higher tumor burden in multiple malignancies including leukemia, lymphoma, and multiple myeloma, which is likely to be associated with greater expansion of T cell populations and synchronous activation with BiTEs. Please refer to the Investigator’s Brochure for additional information.**

Infusion reactions may be clinically indistinguishable from manifestations of CRS. Throughout the infusion with AMG 427 and at least **12** hours after the start of infusion, monitor subjects intensively for clinical signs (eg, fever, hypotension, tachycardia, dyspnea, tremors) and laboratory changes (eg, increase **in transaminases, C-reactive protein [CRP], lactate dehydrogenase [LDH], ferritin, D-dimer, and erythrocyte sedimentation rate [ESR]**) which may be related to CRS. Cytokine release syndrome may be clinically associated with the development of fever, nausea, chills, hypotension, tachycardia, asthenia, headache, rash, scratchy throat, dyspnea, **and ICANS/neurotoxicity** as a consequence of systemic release of cellular cytokines such as TNF, **IL-1Ra**, IL-2, IL-3, IL-4, and IL-6 (**Morris et al, 2021; Winkler et al, 1999**). Potentially life-threatening complications of CRS include cardiac dysfunction, adult respiratory distress syndrome, renal and/or hepatic failure, and disseminated

intravascular coagulation (Lee et al, 2014) and **ICANS/neurotoxicity which may occur concurrently or immediately following CRS.**

Grading of CRS should be performed according to the guidelines provided in **Table 6** and management of CRS should be performed according to the guidelines provided in **Table 7** (based on the adopted grading system referenced in Lee et al, 2019).

Table 6. Cytokine Release Syndrome Grading (ASTCT; Lee et al, 2019)

CRS Parameter	Grade 1	Grade 2	Grade 3	Grade 4
Fever ^a	Temperature $\geq 38^{\circ}\text{C}$	Temperature $\geq 38^{\circ}\text{C}$	Temperature $\geq 38^{\circ}\text{C}$	Temperature $\geq 38^{\circ}\text{C}$
		With		
Hypotension	None	Not requiring vasopressors	Requiring a single vasopressor (not including vasopressin)	Requiring multiple vasopressors (not including vasopressin)
		And/or ^b		
Hypoxia	None	Requiring low-flow (≤ 6 L/minute) nasal cannula or blow-by	Requiring high-flow nasal cannula (> 6 L/min), facemask, non-rebreather mask, or Venturi mask	Requiring positive pressure (eg, CPAP, BiPAP, intubation and mechanical ventilation)

ASTCT = American Society for Transplantation and Cellular Therapy; BiPAP = bilevel positive airway pressure; CPAP = continuous positive airway pressure; CRS = cytokine release syndrome

Organ toxicities associated with CRS may be graded according to CTCAE v4.0 but they do not influence CRS grading.

^aFever is defined as temperature $\geq 38^{\circ}\text{C}$ not attributable to any other cause. In subjects who have CRS then receive antipyretic or anticytokine therapy such as tocilizumab or steroids, fever is no longer required to grade subsequent CRS severity. In this case, CRS grading is driven by hypotension and/or hypoxia.

^bCRS grade is determined by the more severe event: hypotension or hypoxia not attributable to any other cause. For example, a subject with temperature of 39.5°C , hypotension requiring 1 vasopressor, and hypoxia requiring low-flow nasal cannula is classified as grade 3 CRS.

Table 7. Management of Cytokine Release Syndrome

Description of CRS Severity ^a	Minimum Expected Intervention	Instructions for Interruption of AMG 427
Fever (temperature $\geq 38^{\circ}\text{C}$) without hypotension and hypoxia	
• Administer symptomatic treatment (eg, paracetamol/acetaminophen for fever).• Administer tocilizumab^b 4 to 8 mg/kg IV over 1 hour (not to exceed 800 mg). If no clinical improvement in signs and symptoms of CRS after the first dose, repeat tocilizumab every 8 hours (maximum of 3 doses in a 24-hour period; maximum total of 4 doses). If improving discontinue tocilizumab. Monitor for CRS symptoms including vital signs and pulse oximetry at least Q2 hours for 12 hours or until resolution, whichever is earlier. If symptoms of grade 1 CRS do not improve after 24 hours consider managing as grade 2.	

Page 1 of 4

Footnotes defined on next page of the table

Table 7. Management of Cytokine Release Syndrome

Description of CRS Severity ^a	Minimum Expected Intervention	Instructions for Interruption of AMG 427

Fever (temperature $\geq 38^{\circ}\text{C}$) with:
 
 • Hypotension not requiring vasopressor AND/OR • Hypoxia requiring low-flow ≤ 6 L/min nasal cannula or blow-by 	
Administer:
 
 • Symptomatic treatment (eg, paracetamol/ acetaminophen for fever) • Tocilizumab^b 8 mg/kg IV over 1 hour (not to exceed 800 mg). If no clinical improvement in signs and symptoms of CRS after the first dose, repeat tocilizumab every 8 hours (maximum 3 doses in a 24-hour period; maximum total of 4 doses). If improving discontinue tocilizumab. • Dexamethasone 10 mg IV up to 3 times a day. Continue corticosteroids until the severity is grade 1 or less. If not improving manage as grade 3 below. • Supplemental oxygen when oxygen saturation is $< 90\%$ on room air • Intravenous fluids or low dose vasopressor for hypotension when systolic blood pressure is < 100 mmHg. Persistent tachycardia (eg, > 120 bpm) may also indicate the need for intervention for hypotension. 
Monitor for CRS symptoms including vital signs and pulse oximetry at least Q2 hours for 12 hours or until resolution to CRS grade ≤ 1 for at least 24 hours prior to the next dose of AMG 427.
 
For subjects with extensive co-morbidities or poor performance status, manage per CRS guidance below.
	
If hypotension worsens or persists 2 hours after adequate medical management, interrupt AMG 427 until CRS is grade ≤ 1 for at least 24 hours prior to the next dose of AMG 427. Refer to re-start criteria below for CRS grade 3. If symptoms progress to grade 3 criteria, see row below. Permanently discontinue AMG 427 if there is no improvement to CRS \leq grade 1 within 7 days.

Footnotes defined on next page of the table

Table 7. Management of Cytokine Release Syndrome

Description of CRS Severity ^a	Minimum Expected Intervention	Instructions for Interruption of AMG 427

Fever (temperature $\geq 38^{\circ}\text{C}$) with:
 
 • Hypotension requiring a single vasopressor (not including vasopressin) AND/OR • Hypoxia requiring high-flow (> 6 L/min) nasal cannula, facemask, nonrebreather mask, or Venturi mask 	
Admit to intensive care unit (ICU) for close clinical and vital sign monitoring per institutional guidelines.
 
 • Tocilizumab^b 8 mg/kg IV over 1 hour (not to exceed 800 mg). If no clinical improvement in signs and symptoms of CRS after the first dose, repeat tocilizumab every 8 hours (maximum 3 doses in a 24-hour period). If improving discontinue tocilizumab. 
Administer dexamethasone 10-20 mg up to three times a day. If improving manage as appropriate grade above and continue corticosteroids until severity is grade 1 or less, then taper as clinically appropriate.
 
Consider methylprednisolone up to 1000 mg or as per institutional practice.
	
Subjects who experience CRS grade 3 should have next dose delayed until CRS resolves to grade ≤ 1 for at least 24 hours prior to the next dose of AMG 427 (including isolated lab abnormalities and organ toxicity labs, except for LFTs, which must resolve to grade 2 or less), and should have next dose(s) reduced by one-half or more, if given on scheduled day (please consult with the study medical monitor).
 
Permanently discontinue AMG 427 if there is no improvement to CRS \leq grade 2 within 5 days or CRS \leq grade 1 within 7 days.
 
Permanently discontinue AMG 427 if CRS grade 3 occurs at the initial run in dose (ie, at MTD1).

Footnotes defined on next page of the table

Table 7. Management of Cytokine Release Syndrome

Description of CRS Severity ^a	Minimum Expected Intervention	Instructions for Interruption of AMG 427

 • Fever (temperature $\geq 38^{\circ}\text{C}$) with: • Hypotension requiring multiple vasopressors (excluding vasopressin) AND/OR • Hypoxia requiring positive pressure (eg, CPAP, BiPAP, intubation and mechanical ventilation) 	
Admit to ICU for close clinical and vital sign monitoring per institutional guidelines.
 
 • Tocilizumab^b 8 mg/kg IV over 1 hour (not to exceed 800 mg). If no clinical improvement in signs and symptoms of CRS after the first dose, repeat tocilizumab every 8 hours (maximum 3 doses in a 24-hour period). If improving discontinue tocilizumab. 
Administer methylprednisolone up to 1000 mg once per day for 3 days. If improving manage as appropriate grade above and continue corticosteroids until severity is grade 1 or less then taper as clinically appropriate.
 
If not improving consider methyl prednisolone 1000 mg two to three times a day or alternate therapy.
	
Immediately stop the infusion and permanently discontinue AMG 427 therapy.

Page 4 of 4

BiPAP = bilevel positive airway pressure; CPAP = continuous positive airway pressure; CRS = Cytokine Release Syndrome; ICU = intensive care unit;

IL-6 = interleukin 6; IL-6R = interleukin 6 receptor; IV = Intravenous; LFT(s) = liver function test(s); MTD = maximum-tolerated dose

^a Grading system for CRS (Lee et al, 2019)

^b If tocilizumab is not available, another IL-6/IL-6R inhibitor eg, siltuximab may be used per institutional practice for CRS.

Re-start of treatment after CRS:

Please refer to the general guidance for re-start of treatment after adverse events in Section [6.2.1.4](#)

For grade 3 and 4 CRS, please see Section [6.2.1.3](#) for DLT considerations.

Immune-effector Cell-associated Neurotoxicity Syndrome (ICANS):

Immune-effector cell-associated neurotoxicity syndrome (ICANS) typically manifests as a toxic encephalopathy and starts with word-finding difficulty, confusion, dysphasia, aphasia, impaired fine motor skills, and somnolence. In more severe cases, seizures, motor weakness, cerebral edema and coma have been noted. The majority of patients who develop clinical features of ICANS will have had preceding CRS. Cytokine release syndrome can, therefore, be considered an ‘initiating event’ or cofactor for ICANS. Neurotoxicity generally occurs after the symptoms of CRS have subsided, although, less frequently, concurrent presentation of CRS and ICANS can occur. Similar to CRS, ICANS is reversible in most patients with no permanent neurological deficits (Schuster et al, 2019; Neelapu et al, 2018; Santomasso et al, 2018; Gust et al, 2017).

For this trial, ICANS will be managed using the criteria referenced in the American Society for Transplantation and Cellular Therapy (ASTCT) Consensus Grading Criteria for ICANS associated with immune effector cells (Lee et al, 2019). While the grading system has been developed in large part from CAR-T therapies, symptoms of ICANS may be shared among immune effector-cell associated therapies such as BiTE[®] molecules. Although there may be a wide range of symptoms associated with ICANS, subjects may have a stereotypic course of a specific set of symptoms. The earliest manifestations of ICANS are tremor, dysgraphia, mild difficulty with expressive speech (especially in naming objects), impaired attention, apraxia, and mild lethargy.

ICANS grade is determined by the most severe event (eg, depressed level of consciousness, seizure, motor findings, raised intracranial pressure [ICP]/cerebral edema) not attributable to any other cause. Refer to the immune effector cell-associated encephalopathy (ICE) score below for grading of ICANS.

ICE Assessment Tool

- Orientation: Orientation to year, month, city, hospital: 4 points
- Naming: ability to name 3 objects (eg, point to clock, pen, button): 3 points

- Following commands: ability to follow simple commands (eg, “Show me 2 fingers” or “Close your eyes and stick out your tongue”): 1 point
- Writing: ability to write a standard sentence (eg, “Our national bird is the bald eagle”): 1 point
- Attention: ability to count backwards from 100 by 10: 1 point

ICE scoring

- 7-9, grade 1
- 3-6, grade 2
- 0-2, grade 3
- 0 due to subject unarousable and unable to perform ICE assessment, grade 4

Table 8. ASTCT Immune Cell-associated Neurotoxicity Syndrome (ICANS) Consensus Grading for Adults

Neurotoxicity Domain ^a	Grade 1	Grade 2	Grade 3	Grade 4
ICE score ^b	7-9	3-6	0-2	0 (subject is unarousable and unable to perform ICE)
Depression level of consciousness ^c	Awakens spontaneously	Awakens to voice	Awakens only to tactile stimulus	Subject is unarousable or requires vigorous or repetitive tactile stimuli to arouse. Stupor or coma
Seizure	N/A	N/A	Any clinical seizure focal or generalized that resolves rapidly or nonconvulsive seizures on EEG that resolve with intervention	Life-threatening prolonged seizure (> 5 min); or repetitive clinical or electrical seizures without return to baseline in between
Motor findings	N/A	N/A	N/A	Deep focal motor weakness such as hemiparesis or paraparesis
Elevated ICP/cerebral edema	N/A	N/A	Focal/local edema on neuroimaging ^d	Diffuse cerebral edema on neuroimaging; Decerebrate or decorticate posturing; or Cranial nerve VI palsy; or Papilledema; or Cushing’s triad

ASTCT = American Society for Transplantation and Cellular Therapy; CTCAE = Common Terminology Criteria for Adverse Events; EEG = electroencephalogram; ICANS = immune-effector cell-associated neurotoxicity syndrome; ICE = immune effector cell-associated encephalopathy; ICP = intracranial pressure; N/A = not applicable.

- ^a Other signs and symptoms such as headache, tremor, myoclonus, asterixis, and hallucinations may occur and could be attributable to immune effector-cell engaging therapies. Although they are not included in this grading scale, careful attention and directed therapy may be warranted.
 - ^b A subject with an ICE score of 0 may be classified as grade 3 ICANS if awake with global aphasia, but a subject with an ICE score of 0 may be classified as grade 4 ICANS if unarousable.
 - ^c Depressed level of consciousness should be attributable to no other cause (eg, no sedating medication).
 - ^d Intracranial haemorrhage with or without associated edema is not considered a neurotoxicity feature and is excluded from ICANS grading. It may be graded according to CTCAE v4.0.
- Source: Lee et al, 2019

Assessment and Supportive Care Recommendations (all grades)

- Neurologic assessment and grading at least twice a day to include cognitive assessment and motor weakness
- Magnetic resonance imaging (MRI) of the brain with and without contrast (or brain computed tomography [CT] if MRI is not feasible) for \geq grade 2 neurotoxicity
- Neurology consultation at first sign of neurotoxicity
- Conduct electroencephalogram (EEG) for seizure activity for \geq grade 2 neurotoxicity
- Aspiration precautions; IV hydration
- Use caution when prescribing medications that can cause CNS depression (aside from those needed for seizure prophylaxis/treatment)

Table 9. Assessment and Supporting Care Recommendations

Treatment by Grade	No Concurrent CRS	Additional Therapy if Concurrent CRS
Grade 1	
 • Supportive care • If neurotoxicity is observed within 6 hours of dosing, consider anakinra 100 mg subcutaneously every 12 hours for up to 7 days (or another IL-1 receptor inhibitor per institutional practice). 	
In the setting of grade \geq 3 CRS with hypotension, tocilizumab 8 mg/kg IV over 1 h (not to exceed 800 mg/dose)
 
If neurotoxicity is observed within 6 hours of dosing, consider anakinra 100 mg subcutaneously every 12 hours for up to 7 days (or another IL-1 receptor inhibitor per institutional practice).

Grade 2 ^c	
 • Supportive care • Dexamethasone 10 mg IV x 1. Can repeat every 6 hours or methylprednisolone 1 mg/kg IV every 12 h if symptoms worsen. • Consider Anakinra 100 mg subcutaneously every 12 hours for up to 7 days (or another IL-1 receptor inhibitor per institutional 	
Anti-IL-6 therapy as per grade 1
 
Consider transferring subject to ICU if neurotoxicity associated with grade \geq 2 CRS
 
Consider Anakinra 100 mg subcutaneously every 12 hours for up to 7 days (or another IL-1 receptor inhibitor per

Treatment by Grade	No Concurrent CRS	Additional Therapy if Concurrent CRS
	practice) if neurotoxicity is observed within 6 hours of dosing.	institutional practice) if neurotoxicity is observed within 6 hours of dosing.
Grade 3 ^c	
 Supportive care Dexamethasone 10 mg IV every 6 h or methylprednisolone, 1 mg/kg IV every 12 h^a Consider Anakinra 100 mg subcutaneously every 12 hours for up to 7 days if neurotoxicity is observed within 6 hours of dosing. Consider repeat neuroimaging (CT or MRI) every 2-3 days if subject had persistent grade ≥ 3 neurotoxicity. 	Anti-IL-6 therapy as per grade 1 Consider Anakinra 100 mg subcutaneously every 12 hours for up to 7 days if neurotoxicity is observed within 6 hours of dosing
Grade 4 ^c	
 ICU care, consider mechanical ventilation for airway protection. High-dose corticosteroids^{a,b} Consider Anakinra 100 mg subcutaneously every 12 hours for up to 7 days (or another IL-1 receptor inhibitor per institutional practice) if neurotoxicity is observed within 6 hours of dosing Consider repeat neuroimaging (CT or MRI) every 2-3 days if subject has persistent grade ≥ 3 neurotoxicity. Treat convulsive status epilepticus per institutional guidelines. 	Anti-IL-6 therapy as per grade 1 Consider Anakinra 100 mg subcutaneously every 12 hours for up to 7 days (or another IL-1 receptor inhibitor per institutional practice) if neurotoxicity is observed within 6 hours of dosing.

CRS = cytokine release syndrome; CT = computed tomography; ICU = intensive care unit; IL-1 = interleukin 1; IL-6 = interleukin 6; IV = intravenous; MRI = magnetic resonance imaging.

^a Antifungal prophylaxis should be strongly considered in subjects receiving steroids for the treatment of CRS and/or neurotoxicity.

^b For example, methylprednisolone IV 1000 mg/day for 3 days, followed by rapid taper at 250 mg every 12 hours for 2 days, and 60 mg every 12 hours for 2 days.

^c Diagnostic lumbar puncture for grade 3-4 neurotoxicity; consider for grade 2.

^d Repeat tocilizumab every 8 hours as needed if not responsive to IV fluids or increasing supplemental oxygen. Limit to a maximum of 3 doses in a 24-hour period; maximum total of 4 doses

Tumor Lysis Syndrome

Subjects with AML and WBC < 10 000/mcL (or 10 cells x 10⁹/L) are considered to be at low risk for tumor lysis syndrome. White blood cells (WBC) > 10 000/mcL and < 50 000/mcL are considered to be at intermediate risk, and subjects with WBC > 50 000/mcL are considered at high risk. This protocol requires that subjects have a maximum WBC count of 15 000/mcL or 15 cells x 10⁹/L.

Additional high risk features include baseline uric acid > 450 $\mu\text{mol/L}$ (7.5 mg/dL), serum creatinine > 1.4 mg/dL, and lactate dehydrogenase (LDH) greater than the ULN.

Subjects with intermediate risk WBC count and elevated baseline uric acid (> 450 $\mu\text{mol/L}$), serum creatinine > 1.4 mg/dL, or LDH greater than ULN will be recommended to receive allopurinol prophylaxis. Typical dosing is 600 - 800 mg/day administered twice a day (BID) or 3 times a day (TID) and should begin 3 days before the first dose of study drug. Subjects should be well hydrated and supplemented with intravenous fluid as clinically indicated.

For grade 3 and 4 TLS, please see Section 6.2.1.3 for DLT considerations.

Infection Prophylaxis

Subjects who may experience neutropenia for 7 days or longer are at a high risk for infectious complications. As appropriate, these subjects should be administered prophylactic antibacterial (eg, fluoroquinolones), antifungal, and antiviral medications. These subjects should be monitored for early signs of breakthrough infections after the initiation of antibacterial therapy to prompt additional evaluation and possible therapy modification.

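### Table 7's grade 2 CRS row offers a low-dose vasopressor although Table 6 puts hypotension that requires one at grade 3, which invites under-grading where the grade decides a DLT

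*Protocol*

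**What the plan says.** **Grading.** In Protocol Table 6, hypotension that needs no vasopressor is grade 2. Hypotension that needs a single vasopressor is grade 3; vasopressin is not counted, and low doses are not exempted. Footnote b gives an example: fever with "hypotension requiring 1 vasopressor, and hypoxia requiring low-flow nasal cannula is classified as grade 3 CRS". Section 6.6 states that "Grading of CRS should be performed according to the guidelines provided in" Table 6, and assigns management to Table 7. Section 6.2.1.3 also sends CRS grading to Table 6.

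**Management.** The second row of Table 7 is described as "Hypotension not requiring vasopressor" and/or hypoxia on low-flow oxygen. Its minimum expected intervention includes "Intravenous fluids or low dose vasopressor for hypotension when systolic blood pressure is < 100 mmHg". The row has three exits:

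- in the dexamethasone bullet, "If not improving manage as grade 3 below";
- in the interruption column, "If symptoms progress to grade 3 criteria, see row below";
- "If hypotension worsens or persists 2 hours after adequate medical management", dosing is interrupted and the grade 3 re-start criteria apply.

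**Consequences.** Under Section 6.2.1.3, grade 2 CRS is a DLT only if it has not resolved to grade 1 or less within 7 days. Grade 3 CRS at the run-in dose is a DLT once MTD1 has been defined, and so are two separate grade 3 events. Section 6.2.1.4 lists both grade 3 situations under permanent discontinuation. SAP Section 5 takes DLT status from the investigator's flag on the Events CRF.

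**The concern.** The vasopressor is an alternative to fluids, not a step after fluids fail, and it is offered to patients described as not requiring one. No sentence in the row, the DLT list or the SAP says that requiring this drug moves the event to grade 3. A site that follows the row could start it, see the pressure recover and leave the event at grade 2.

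The DLT is a primary endpoint. It feeds the BLRM and the pause rule for the expansion (Protocol Section 10.3). The Amendment 7 rationale says the pause rule was rebased on DLTs so that qualifying grade 2 and 3 CRS events would count, in an amendment prompted by a fatal CRS event. CRS is common here: 42 of 53 subjects (79.2%) in Section 2.2.4. The grading system also changed between cohorts (SAP Section 9.6.2), so the management row and the current grading table ought to agree exactly.

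**Working it through.** **1. The two tables.** Table 6 turns on whether a vasopressor is *required*. Table 7 *offers* one in the row for patients who do not require it. If the agent is vasopressin there is no conflict, because Table 6 does not count it. For any other agent the row conflicts with its own description. The first two exits depend on non-improvement or on reaching grade 3 criteria. Hypotension that the drug controls prompts neither unless the reader goes back to Table 6.

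**2. What the recorded grade decides.** Take an event treated with one low-dose vasopressor other than vasopressin and resolved to grade 1 or less within 5 days.

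| Situation | Recorded grade 2 | Recorded grade 3 |
|---|---|---|
| Run-in dose, MTD1 already defined | Not a DLT | DLT under the run-in bullet; permanent discontinuation |
| Subject already had one grade 3 CRS event | Not a DLT | DLT as second event; permanent discontinuation |
| Next dose | Grade 3 re-start criteria only if hypotension worsens or persists at 2 hours | Delayed, and halved or more if given on the scheduled day |
| Setting | No ICU requirement | ICU admission |

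The run-in line applies in the expansion only if dose steps are used (Section 6.2.1.1). If siltuximab was given, the grade also enters its progression-to-grade-3 count (Section 10.3).

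**3. The 12-hour exception.** Section 6.2.1.3 exempts grade 3 infusion reactions, including CRS, that are managed successfully and resolve within 12 hours. The exemption is attached to the general rule for grade 3 to 5 non-hematologic toxicity. Whether it also overrides the run-in and repeat-event bullets is not stated. If it does, the grade changes those DLT calls only for events longer than 12 hours. If the general rule applies to CRS at all, a grade 3 event beyond 12 hours could be a DLT outside run-in too. The discontinuation list in Section 6.2.1.4 has no 12-hour exception.

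**4. The expansion pause rule.** Inputs from Section 10.3: prior Beta(0.40, 1.60); pause if P(DLT rate > 0.20) > 0.80; looks every 6 subjects. With x DLTs in n subjects the posterior is Beta(0.4 + x, 1.6 + n − x).

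*Reproduction.* The rule gives boundaries 3, 4, 6, 7, 9, 10, 11, 13 at n = 6, 12, …, 48, as in Table 26. An exact binomial recursion gives R/R early stopping of 3.8%, 34.0%, 78.9% and 97.4% at true rates 0.10, 0.20, 0.30 and 0.40, as in Table 27.

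*One DLT more or less.*

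| n | x | P(rate > 0.20) | Action |
|---|---|---|---|
| 6 | 2 | 0.707 | continue |
| 6 | 3 | 0.914 | pause |
| 12 | 3 | 0.608 | continue |
| 12 | 4 | 0.821 | pause |

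*Chance of being exactly at the first boundary.* P(X = 3 | n = 6) = 20 p³(1 − p)³, which is 8.2%, 18.5% and 27.6% at p = 0.20, 0.30 and 0.40. This counts DLTs of any kind.

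*Recovery at the next look.* If 3 true DLTs are recorded as 2 at n = 6, the boundary of 4 at n = 12 is reached if at least 2 of the next 6 subjects have a recorded DLT. With those counted correctly, 1 − (1 − p)⁶ − 6p(1 − p)⁵ gives 34%, 58% and 77% at p = 0.20, 0.30 and 0.40.

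**The case against.** The best defense is that the grading rule exists, is explicit and prevails. Table 6 defines grade 3, footnote b illustrates it, the next row of Table 7 opens with the same criterion, and the disputed row points there. On this view the left column describes how the patient presents and the middle column says what to do next, so a patient who comes to need a vasopressor simply moves down a row. Vasopressin fits the row as it stands. In addition, the DLRT reviews concomitant medications and vital signs (Section 10.4.2), and meets for every sixth expansion subject.

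Most of this stands, and it limits the point to an inconsistency that invites error. It does not remove it. The cell itself authorizes the drug that marks the next grade. No rule tells the DLRT to regrade an event, and the DLT flag comes from the site.

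Three stronger readings are tempting, and the documents do not support them:

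- *That grade 3 is undefined, or that Table 7 overrides Table 6.* Sections 6.2.1.3 and 6.6 both assign grading to Table 6.
- *That any vasopressor given makes the event grade 3.* Table 6 says required, so a drug given when fluids would have sufficed is not automatically grade 3.
- *That DLTs are known to be under-counted, or that a missed DLT defeats the pause rule.* No misgrading rate is given, and the percentages above are not such a rate. A missed pause is often only delayed by one look.

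**Conclusion.** The inconsistency is in the current text and should be corrected. Its reach is narrow but falls on a primary endpoint: the DLT and discontinuation calls for grade 3 CRS at run-in after MTD1 is defined, and for a second grade 3 event. The DLT consequence is subject to the unresolved 12-hour exception.

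The size can be stated only per event. One uncounted DLT reverses the first expansion decision when the true count is exactly 3 of 6 (0.914 against 0.707, limit 0.80). At true rates of 0.20 to 0.40 the pause would still be reached at 12 subjects with probability 34% to 77%. These figures assume independent subjects with a common DLT rate, one hidden event and correct counting afterwards. They do not estimate how often an event would be misgraded. The stated values in Tables 26 and 27 are correct and do not change.

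**What to change.** In the grade 2 row of Table 7, limit the hypotension bullet to intravenous fluids or vasopressin, keeping the same systolic trigger, and add: *If hypotension requires a vasopressor other than vasopressin, at any dose, the event is at least grade 3 under Table 6; manage it by the row for that grade.* Keep the word *requires*. Replacing it with *is given* would change the adopted grading standard. Add a cross-reference to Table 6 in the CRS bullets of Section 6.2.1.3.

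The cost is a reworded table cell and one cross-reference. No new data are needed, because concomitant medications are already collected, and patients who need a vasopressor still receive one under the grade 3 row. The downside is that some events now recorded as grade 2 would count as grade 3, which adds some DLTs, run-in discontinuations and ICU admissions. Table 6 already intends these.
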